9.2.3.4 Sub-Populations

Five subpopulations will be considered in order to meet the objectives of the study:

- Elderly NVAF patients stratified on age-group (≥ 80 years old);
- NVAF patients having a history of coronary arterial disease (CAD);
- NVAF frail patients;
- NVAF patients having an active cancer;
- NVAF patients reported with previous stroke.

9.2.3.5 Stratification groups

Stratification groups will be considered:

- Age groups (<80 , $80-90$, >90 years old);
- Modified CHAD₂DS₂VASC score strata (Low risk / Moderate risk/ High risk);
- Patients having a history of stroke (Ischemic / Hemorrhagic);
- Patients having a malnutrition (Yes / No);
- Patients at risk of falls identified by an algorithm adapted to SNDS data (Yes / No);
- Frail patients identified by Claims based Frailty Index (CFI) adapted to SNDS data (Yes / No);
- NVAF patients with one or more comorbidities identified by age adjusted Charlson comorbidity index (ACCI) adapted to SNDS data (Yes / No);
- Patients having a morbid obesity (Yes / No);
- Patients with a history of major bleeding;
- Patient with at least one visit to a nursing home;
- Patients with a history of dementia.

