3.7.4 Stratified analyses

Secondary objectives analyses will be stratified on:

- Patients having a malnutrition,
- Patients at risk of falls identified by an algorithm adapted to SNDS data,
- Frail patients identified by Claims based Frailty Index (CFI) adapted to SNDS data,
- AF Patients with one or more comorbidities identified by age-adjusted Charlson comorbidity index (ACCI) adapted to SNDS data,
- Patients having a morbid obesity,
- Patients with a history of ischemic or hemorrhagic stroke,
- Patients with a history of major bleeding,
- Patient with at least one visit to a nursing home
- Patients with a history of dementia

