7.1 Background

Atrial fibrillation (AF) is a heart rhythm disorder caused by abnormal electrical signals from the atria and is characterized by ineffective atrial contraction and irregular heartbeats. AF can occur in three forms: paroxysmal (episodes lasting less than 7 days), persistent or permanent (lasting more than 7 days) and irreversible (1).

Among patients with AF, more than one-third have associated valve disease, characterized by mitral stenosis or valve prosthesis (1). In this case, AF is called "valvular" (2). Conversely, in patients without associated valvular pathology, AF is said to be "non-valvular".

In France, two-thirds of AF patients are 75 years of age and older. The prevalence of AF is about 1% of the general population and increases with age to reach 10% of the population aged 80 years and over. The male/female sex ratio of prevalent cases is 3:2 (3). The absolute number of cases is equivalent between men and women because of the higher life expectancy in women (4).

Several pathophysiological mechanisms, including blood flow stasis, prothrombotic state, and hypercoagulability induced by AF, can lead to stroke (5). Clinical signs may include shortness of breath at rest, fatigue, palpitations, or chest pain. AF accounts for approximately 15% of all strokes (6).

The therapeutic management aims to prevent thromboembolic complications (risk multiplied by 5), in particular the occurrence of ischemic stroke, to reduce symptoms, to prevent recurrence of AF using antiarrhythmic treatment and to improve the quality of life of patients (4). The 2014 Guidelines of the French National Authority for Health recommend initiating an oral anticoagulant (OAC) in AF patients to prevent the risk of stroke in the event of a high thromboembolic risk identified by a CHA2DS2-VASC score greater than or equal to 2. If the score is equal to 1, the initiation is to be discussed according to risk factors. Among the OACs, the antivitamins K (VKA) (warfarin, acenocoumarol – and fluindione until 2017) were considered as the reference drugs until 2017; the direct oral anticoagulant (DOAC) including direct factor Xa inhibitors (rivaroxaban and apixaban) and direct thrombin inhibitor (dabigatran) could be prescribed as an alternative (4). Recommendations concerning the good use of OACs has been updated in 2018 (5). **Since then, DOAC can also be prescribed as a first-line treatment in non-valvular AF (NVAF) patients.**

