Solid metastatic tumor (for ACCI derivation)	
Binary variable (Yes / No)
 
Equals to “Yes” if the patient meets any criterion below on or in the 2 years prior to the index date:
 
 – Is hospitalized at least once with any discharge diagnosis (i.e., main, related or associated diagnosis) of metastatic tumor 
ICD-10 codes : C77.x, C78.x, C79.x, C80
 
OR
 
 – Is covered by the LTD status for metastatic tumor at least one day 
ICD-10 codes : C77.x, C78.x, C79.x, C80
 
Equals to “No” in other cases

Age adjusted Charlson Cormordity Index (ACCI) adapted to the SNDS data	
Continuous variable (point)
 
Derived based on (20,23)
 
Equals to the sum of:
 
 ○ 0 point if the variable History of diabetes equals to “Yes” ○ 0 point if the variable History of diabetes with complications equals to “Yes” ○ 0 point if the variable History of myocardial infarction equals to “Yes” ○ 2 points if the variable Heart failure equals to “Yes” ○ 1 point if the variable Peripheral vascular disease equals to “Yes” ○ 1 point if the variable Cerebrovascular disease equals to “Yes” ○ 1 point if the variable Moderate-to-severe renal disease equals to “Yes” ○ 2 points if the variable Mild liver disease equals to “Yes” ○ 3 points if the variable Moderate-to-severe liver disease equals to “Yes” ○ 1 point if the variable Chronic pulmonary disease equals to “Yes” ○ 2 points if the variable Dementia equals to “Yes”

	
 ○ 0 point if the variable Connective tissue disease equals to "Yes" ○ 0 point if the variable Ulcer disease equals to "Yes" ○ 2 points if the variable Hemiplegia equals to "Yes" ○ 1 point if the variable HIV-AIDS equals to "Yes" ○ 2 points if the variable Any tumor (including lymphoma and leukemia) equals to "Yes" ○ 11 points if the variable Solid metastatic tumor equals to "Yes" ○ 1, 2, 3, 4, 5 or 6 points if the variable Age is greater or equal than 50, 60, 70, 80 90 or 100 years old, respectively
ACCI group	
Categorical variable (0, 1-2pts / 3-4pts / ≥ 5 pts)
 
Derived based on ACCI define above
 
Equals to:
 
"0" if ACCI is equal to 0 (the patient has no comorbidities)
 
"1-2pts" if ACCI is greater than 0 and less or equal to 2
 
"3-4pts" if ACCI is greater than 2 and less or equal to 4
 
≥ 5pts" if ACCI is greater or equal than 10

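### Read from the age-adjusted Charlson index, the one-or-more-comorbidities flag is essentially a split at age 50, and the four-level index is partly tied to age

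*SAP*

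**What the plan says.** SAP 9.2.3.5 lists as a stratification group "NVAF patients with one or more comorbidities identified by age adjusted Charlson comorbidity index (ACCI) adapted to SNDS data (Yes / No"). Protocol 3.7.4 asks for the same stratum in the secondary-objective analyses: "AF Patients with one or more comorbidities identified by age-adjusted Charlson comorbidity index (ACCI) adapted to SNDS data".

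SAP Table XIII lists the Yes/No variable and refers to Table VI for its definition. Table VI (section 9.4.1) has no variable of that name. It defines only the ACCI and a four-level ACCI group:

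- **Age.** The index adds 1 to 6 "points if the variable Age is greater or equal than 50, 60, 70, 80 90 or 100 years old, respectively".
- **Zero weights.** Examples are "0 point if the variable History of diabetes equals to" Yes and "0 point if the variable History of myocardial infarction equals to" Yes. Complicated diabetes, connective tissue disease and ulcer disease also score 0.
- **Lowest group.** It applies "if ACCI is equal to 0 (the patient has no comorbidities").
- **Top group.** It is labelled as 5 points or more, but its rule requires a score of 10 or more.

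The categorical ACCI is a stratum in shell Tables A12 and A13. It is also a confounder in Table XV, in the groups 0, 1-2, 3-4 and ≥5, beside age as a separate covariate (<80, 80–90, >90). The covariate footnotes of Tables A10 and A11 do not list it.

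**The concern.** A flag for at least one comorbidity should depend on disease. If the score behind it already gives a point to everyone from age 50, disease cannot change the class of those patients. If some diseases score 0, a younger patient who has only those is recorded as having none.

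A Yes/No result reported under this name would then compare patients of roughly 50 and over with a small younger group, and readers would take the contrast as one of comorbidity. The four-level version raises a milder form of the problem where it sits beside age, as a stratum in Tables A12/A13 and as a covariate in Table XV. Separately, the mismatch between label and rule for the top group would leave some patients with no category.

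**Working it through.** The plan gives no figure to reproduce here, because the point concerns a scoring rule. The check applies Table VI as written.

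**Inputs from Table VI.** Age points are 0 below 50, then 1, 2, 3, 4, 5 and 6 from 50, 60, 70, 80, 90 and 100. There are 17 conditions. Five score 0 (diabetes, complicated diabetes, infarction, connective tissue disease, ulcer) and twelve score between 1 and 11. ACCI = age points + disease points.

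**Yes/No flag.** The cut-off is inferred. If 0 means no comorbidities, Yes means ACCI ≥ 1.

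- No disease: age 45 or 49 gives 0 (No); 50 gives 1, 60 gives 2, 70 gives 3, 80 gives 4, 90 gives 5 and 100 gives 6 (all Yes).
- Age 45 with all five zero-weight conditions: 0 + 0 = 0 (No).
- Age 45 with chronic pulmonary disease: 0 + 1 = 1 (Yes). With heart failure: 0 + 2 = 2 (Yes).

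So No can contain only patients under 50, and disease affects the class only below 50.

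**Size of the strata.** SAP 7.1 states that "two-thirds of AF patients are 75 years of age and older" in France. If that carried over to the cohort, about two-thirds would be Yes through age points alone, as a floor. For a fuller range, let f be the share aged 50 or over and q the share of younger patients with a scoring condition. The documents give neither, so I assume f = 0.90–0.98 and q = 0.1–0.5.

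- Share Yes = f + (1 − f)q: from 0.90 + 0.10 × 0.1 = 0.91 to 0.98 + 0.02 × 0.5 = 0.99.
- Share No = (1 − f)(1 − q): from 0.02 × 0.5 = 0.01 to 0.10 × 0.9 = 0.09.
- Share of the Yes group placed there by age whatever their diseases = f / [f + (1 − f)q]: from 0.90/0.95 = 0.947 to 0.98/0.982 = 0.998.

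**Four-level group.** The middle columns give the disease points that lead to each labelled group. The last column gives those that fall in no group under the coded rule (total score 5–9).

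| Age | Age points | 0 | 1-2 | 3-4 | ≥5 (label) | No group as coded |
|---|---|---|---|---|---|---|
| <50 | 0 | 0 | 1–2 | 3–4 | ≥5 | 5–9 |
| 50–59 | 1 | – | 0–1 | 2–3 | ≥4 | 4–8 |
| 60–69 | 2 | – | 0 | 1–2 | ≥3 | 3–7 |
| 70–79 | 3 | – | – | 0–1 | ≥2 | 2–6 |
| 80–89 | 4 | – | – | 0 | ≥1 | 1–5 |
| 90–99 | 5 | – | – | – | any | 0–4 |
| ≥100 | 6 | – | – | – | any | 0–3 |

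Nobody aged 70 or over can be in 0 or 1-2. Under the label, everyone aged 90 or over is in the top group. At 70–79 and 80–89 the split between 3-4 and ≥5 still separates patients by disease.

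**The case against.** The Yes/No cut-off is never written, so the result for the flag rests on inference. That is true. But the sentence equating a score of 0 with no comorbidities is the only rule offered, and a programmer sent to Table VI would have nothing else to follow.

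The zero weights are attributed to cited sources and are no error in a weighted score. That stands. The objection is only to using such a score to say whether any comorbidity is present.

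The strongest reply concerns the Cox models. A reader might infer that the ACCI term merely repeats age and that comorbidity adjustment is lost in the oldest patients. The documents do not support this. At 80–89, under the ≥5 label, the grouping is a clean indicator of any weighted disease, and at 70–79 it separates 0–1 from 2 or more disease points. Only from 90 does it carry nothing. SAP 9.7.4.2 and Table XV also adjust for CHA2DS2-VASc, HAS-BLED, frailty, malnutrition, falls risk, nursing-home stay, earlier stroke, major bleeding, dementia and each concomitant treatment.

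A reader might also infer that no comorbidity-stratified results can be produced. Tables A12/A13 use the four-level index instead of the flag, and they stratify separately by cancer, coronary disease, stroke, dementia, frailty and other conditions. The loss is confined to the one-or-more-comorbidities result.

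**Conclusion.** The point holds for the Yes/No flag. As the only available rule reads, it is essentially a split at age 50. Disease cannot alter the class of anyone aged 50 or over, and a younger patient with only zero-weight conditions is recorded as having none. That follows exactly from Table VI once Yes is taken as ACCI ≥ 1. The 91–99% share rests on the assumed f and q. The two-thirds floor borrows a figure for French AF patients generally, not for the incident non-valvular cohort, and it does not mean that those patients are free of disease.

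For the four-level index the point is narrower. It is partly confounded with age, has a single possible value from 90 under its label, and otherwise remains informative at 70–89. The gap at scores 5–9 is a plain contradiction between label and rule.

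Nothing here reaches the primary objective's five subgroups. The documents also give no basis for saying that the problem falls more heavily on untreated patients; SAP 7.1 notes the lack of recent French data on them.

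**What to change.** 1. Write a rule for the flag in Table VI: Yes if at least one Charlson component is Yes, whatever its weight and without age points. Dropping the age points alone would not be enough, because diabetes or infarction alone would still give No.
2. Remove the parenthesis equating ACCI = 0 with no comorbidities, and change the top-group rule from 10 to 5 to match its label and Table XV.
3. Use the Charlson sum without age points (0, 1-2, 3-4, ≥5) as the comorbidity stratum in Tables A12/A13 and, since age is a separate covariate, in Table XV. Label its 0 group as no weighted condition. ACCI can stay as a descriptive line in Tables A5 and A8.
4. Reconcile Table XV with the covariate footnotes of Tables A10 and A11, so that it is clear whether a Charlson term is in the model.
5. Align Protocol 3.7.4.

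The cost is SAP wording and a one-line protocol clarification. All 17 components are already derived, so no new data are needed. One thing to check is that ACCI now also contributes some age adjustment inside the single <80 band; once its age points go, the team should confirm that the remaining age terms are fine enough there.

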9.3 Data Sources

9.3.1 SNDS

9.3.1.1 Presentation of the databases

The French National Health Data System (*Système National des Données de Santé*, SNDS) is the largest and most comprehensive healthcare dataset available in Europe with a 10-year longitudinal follow up for more than 50 million patients. SNDS includes anonymized administrative and healthcare claims data from the French national health care insurance system databases. In particular data from SNIIIRAM (*Système National d'Information Inter-Régimes de l'Assurance Maladie*) which consist of hospital-discharge summaries (*Programme de Médicalisation des Systèmes d'Information*, PMSI), all outpatients reimbursed health expenditures (*Données de Consommation Inter-Régime*, DCIR) and national death registry including cause of death (CépiDC). SNDS data consist of anonymized data of reimbursed claims for all patients affiliated with of compulsory health insurance providers (the general scheme covers about 86% of France residents, and 14 other schemes cover the rest) and cover about 99% of French residents.

Data from DCIR and data from PMSI have been linked for each patient to allow for follow-up across different settings of care including outpatient practice and hospital admissions related to medicine, surgery and obstetrics. At this time, date of death from the national death registry is linked to the other data for all the periods. Causes of death are progressively integrated (only available for 2013, 2014 et 2015). Healthcare use of the patient can then be tracked for since birth/first residence in France for 10 years even if a subject is not working, changes occupation or retires and irrespective of socioeconomic status. There is no loss to follow up except for emigration.

SNDS contains information on beneficiaries age, sex, region of residence, death date, complementary universal health coverage status, and all outpatient healthcare consumption including all reimbursed prescription drugs identified by their ATC code, the date of delivery, quantity, and brand name. Medical procedures performed on an outpatient basis or in a healthcare institution are identified by the *classification commune des actes médicaux* (CCAM, or common classification of medical procedures), laboratory procedures are identified by the *nomenclature des actes de biologie médicale* (NABM, clinical pathology test nomenclature) and paramedical or medical visits are identified by the *nomenclature 27nité27le des actes professionnels* (NGAP, General nomenclature of professional procedures).

SNDS informs about the presence of long-term chronic disease (LTD) status, eligible for 100% reimbursement of healthcare expenditure; the date of the LTD diagnosis; and its nature, coded according to the ICD-10. Registration for LTD is requested by the patient's general practitioner, and diagnoses are approved by the health insurance medical consultant. Registration is not mandatory. It may be missing, for instance, if the medical expenses are already covered by another chronic disease or the treatment is not expensive.

Through the PMSI, the SNDS also includes medical summaries of all hospitalizations from all private or public hospitals, including the date of stay, medical procedures and costly innovative drugs Non-English text or implantable devices during the hospital stay, the primary diagnosis (main reason for admission), related diagnoses (specifies the disease context of the primary diagnosis), and diagnoses related to other comorbidities, all encoded according to the ICD-10. Information on occupational diseases, sick leaves are also available.

9.3.1.2 Main data available

The data available in DCIR and PMSI databases that are of importance for this study are as follows:

- Administrative data used for sociodemographic, including:
 - o Date of birth (month and year);
 - o Date of death;
 - o Sex;
 - o City, department and region of residence;
 - o CMU-C;
 - o Aid for complementary health care (ACS) for elderly patients.
- Outpatient care data, including:
 - o Health professionals visited, medical specialty for physicians, dates of visits;
 - o Dates of dispensation, dates of reimbursement, type and number of services carried out by the health professional, reimbursed costs and costs paid by the patients for the associate cares;
 - o Drugs coded according to ATC and CIP classifications;
 - o Medical and technical acts coded according to CCAM;
 - o Biological acts coded according to NABM;
 - o Medical devices coded according to LPPR;
 - o Medical transportations;
 - o Sick leaves;
- Inpatient care data, including:
 - o Type of stay coded according to DRG;
 - o Localization, type and identifier of hospitals;
 - o Dates and reasons for admissions and discharges;
 - o Main, related and significant associated diagnoses of admissions coded according to ICD-10;
 - o Drugs dispensed at hospital and costly innovative drugs administered during admissions, both coded according to ATC and the common unit of dispensation (28nité commune de dispensation, UCD) classification;
 - o Medical and biological acts performed during admissions and coded according to CCAM and NABM, respectively;
 - o Other information such as stays in resuscitation units or intensive cares.
- Medical data, including:
 - o Presence of a LTD status, start and end dates of LTD coverage and nature of LTDs coded according to ICD-10.

9.4 Derived Variables

9.4.1 Derived Variables for the Selection of the Study Populations

First, all the variables representing the inclusion criteria will be derived for each patient (Table I).

Table I. Derived variables for the selection of the population – Inclusion criteria

Variable	Definition
Atrial fibrillation diagnosis	
Binary variable (Yes/No)
 
Equals to “Yes” if the patient meets any criterion below:
 
 – Is hospitalized at least once with any discharge diagnosis (i.e., principal, related or associated diagnosis in PMSI-MSO) of atrial fibrillation during the study (historical or inclusion) period 
ICD-10 codes: I48
 
OR
 
 – Is covered by the LTD status for atrial fibrillation at least one day during the study (historical or inclusion) period 
ICD-10 codes: I48
 
Equals to “No” in other cases

Age ≥18 years	
Binary variable (Yes / No)
 
Derived based on the date of birth attributed to the patient after cleaning the data extraction
 
Equals to “Yes” if the absolute difference between the year of index date and the year of birth is upper than or equal to 18 years
 
See also Data Management Plan in section Error! Reference source not found.
 
Equals to “No” in other cases

Second, a validated and published algorithm using a predictive model developed by Billonnet et al. (16) will be applied for the identification of AF indications in outpatients initiating OAC (Table II).

Table II. Derived variables for the selection of the population – Identification of AF outpatients initiating OAC

Variable	Definition
New users of OACs (for AF outpatients)	
Binary variable (Yes/No)
 
Equals to “Yes” if the patient receives at least one reimbursement of an OAC (VKA, apixaban, rivaroxaban or dabigatran) during the inclusion period, without use of any OAC in the 24 months prior the first date of OAC delivery

Variable	Definition
	
ATC codes: B01AA, B01AF02, B01AF01, B01AE07
 
Equals to “No” in other cases

Patients initiating OAC for a lower limb orthopaedic indication	
Binary variable (Yes/No)
 
Equals to “Yes” if the patient receives at least one reimbursement of orthopedic procedure (osteoarticular or muscular) of the lower limb (including hip/knee replacement) as corresponding to the indication of primary prevention of venous thromboembolic events, during a 6-week period before the first date of OAC delivery
 
DRG code: D02
 
Equals to “No” in other cases

Confirmed AF	
Binary variable (Yes/No)
 
Equals to “Yes” if the patient meets any criterion below:
 
 – Is hospitalized at least once with any discharge diagnosis (i.e. principal, related or associated diagnosis in PMSI-MSO) of atrial fibrillation before the first date of OAC delivery during historical period 
ICD-10 codes: I48
 
OR
 
 – Is covered by an ongoing LTD status for atrial fibrillation before the first date of OAC delivery during historical period 
ICD-10 codes: I48
 
OR
 
 – Had an electrical cardioversion procedure or radiofrequency ablation before the first date of OAC delivery during historical period 
CCAM codes: DERP003, DEPF004, DEPF005
 
Equals to “No” in other cases

Confirmed DVT/PE	
Binary variable (Yes/No)
 
Equals to “Yes” if the patient meets any criterion below:
 
 – Is hospitalized at least once with any discharge diagnosis (i.e. principal, related or associated diagnosis in PMSI-MSO) of PE or DVT during a 6-week period before the first date of OAC delivery 
ICD-10 codes: I26.x, I80.1, I80.2, I80.3, I80.8, I80.9, I81.x, I82.x
 
OR

Variable	Definition
	
 - Had a doppler ultrasound examinations, CT venography, MR venography or pulmonary scintigraphy during a 6-week period before the first date of OAC delivery 
CCAM codes: GFQL007, GFQL006, GFQL005, GFQL002, GLQL002, GFQL001, GFQL004 (pulmonary scintigraphy); EJQM003, DHQM002, EJQM004, EJQM001 (doppler ultrasound examinations); EFQH001, EFQH003, EFQH004, EFQH005, EFQH006, DHQH003 (CT venography); EAQJ001, EBQJ00, EBQJ001, ECQJ001, ELQJ001, EKQJ001, EMQJ001, ELQJ003 (MR venography).
 
Equals to "No" in other cases

Unclassified patients	
Binary variable (Yes/No)
 
Equals to "Yes" if Confirmed AF = "No" and Confirmed DVT/PE = "No"
 
The algorithm will be applied on the unclassified patients. Patients with both confirmed AF and DVT/PE will be excluded.
 
Equals to "No" in other cases

Then, a logistic model included 14 independent covariables will be applied on unclassified patients to identify AF outpatients initiating OAC ([Table III](#)).

Table III. Derived variable for the selection of the population – Covariables included in the logistic model

Variable	Definition
Age	
Categorical variable (<65 years old / 65-74 / 75-79 / ≥80 years old)
 
Derived based on the date of birth attributed to the patient after cleaning the data extraction
 
Equals to:
 
 9. "<65 years old" if the absolute difference between the year of index date and the year of birth is strictly lower than 65 years old 10. "65-74" if the absolute difference between the year of index date and the year of birth is between 65 and 74 years old 11. "75-79" if the absolute difference between the year of index date and the year of birth is between 75 and 79 years old 12. "≥80 years old" if the absolute difference between the year of index date and the year of birth is upper than 80 years old 
See also Data Management Plan in section Error! Reference source not found.

Gender	Binary variable (Female / Male) Equals to the value attributed to the patient after cleaning the data extraction See Data Management Plan in section Error! Reference source not found.
Cardiologist prescriber	Binary variable (Yes / No) Equals to "Yes" if the prescriber of the initiation of the OAC is a cardiologist Code CNAM repository (variable PSE_SPE_COD): 03 Equals to "No" in other cases
Initiation of beta-blockers	Binary variable (Yes / No) Equals to "Yes" if the patient has reimbursements for at least one dispensation at pharmacy of any beta-blockers during the 6 weeks preceding the first date of OAC delivery and with no filled prescription for the medication during the previous 180 days ATC codes: C07xxxx Equals to "No" in other cases
Use of beta-blockers	Binary variable (Yes / No) Equals to "Yes" if the patient has reimbursements for at least one dispensation at pharmacy of any beta-blockers during the 6 weeks preceding the first date of OAC delivery ATC codes: C07xxxx Equals to "No" in other cases
Initiation of antiarrhythmics	Binary variable (Yes / No) Equals to "Yes" if the patient has reimbursements for at least one dispensation at pharmacy of any antiarrhythmics during the 6 weeks preceding the first date of OAC delivery and with no filled prescription for the medication during the previous 180 days ATC codes: C01Bxxx Equals to "No" in other cases
Use of antiarrhythmics	Binary variable (Yes / No) Equals to "Yes" if the patient has reimbursements for at least one dispensation at pharmacy of any antiarrhythmics during the 6 weeks preceding the first date of OAC delivery ATC codes: C01Bxxx Equals to "No" in other cases

Initiation of antihypertensive drugs	
Binary variable (Yes / No)
 
Equals to “Yes” if the patient has reimbursements for at least one dispensation at pharmacy of any antihypertensive drug during the 6 weeks preceding the first date of OAC delivery and with no filled prescription for the medication during the previous 180 days
 
ATC codes: C02xxxx, C03xxxx, C08xxxx, C09xxxx (excluding C03BA08 and C03CA01)
 
Equals to “No” in other cases

Use of antihypertensive drugs	
Binary variable (Yes / No)
 
Equals to “Yes” if the patient has reimbursements for at least one dispensation at pharmacy of any antihypertensive drug during the 6 weeks preceding the first date of OAC delivery
 
ATC codes: C02xxxx, C03xxxx, C08xxxx, C09xxxx (excluding C03BA08 and C03CA01)
 
Equals to “No” in other cases

Holter procedure	
Binary variable (Yes / No)
 
Equals to “Yes” if the patient has reimbursements for at least one Holter procedure during the 6 weeks preceding the first date of OAC delivery
 
CCAM codes: DEQA001, DEQP001, DEQP002, DEQP003, DEQP005, DEQP006
 
Equals to “No” in other cases

Echocardiography procedure	
Binary variable (Yes / No)
 
Equals to “Yes” if the patient has reimbursements for at least one echocardiography procedure during the 6 weeks preceding the first date of OAC delivery
 
CCAM codes: DZQJ001, DZQJ006, DZQJ009, DZQJ010, DZQJ011, DZQM006
 
Equals to “No” in other cases

Thyroid function test	
Binary variable (Yes / No)
 
Equals to “Yes” if the patient has reimbursements for at least one thyroid function test during the 6 weeks preceding the first date of OAC delivery
 
NABM Codes: 1206-1212, 1803.
 
Equals to “No” in other cases

D-dimer blood test	
Binary variable (Yes / No)
 
Equals to “Yes” if the patient has reimbursements for at least one D-dimer blood test during the 6 weeks preceding the first date of OAC delivery

	
NABM codes: 1021, 1022.
 
Equals to "No" in other cases

Hospitalization for arterial thromboembolic event	
Binary variable (Yes / No)
 
Equals to "Yes" if the patient is hospitalized at least once with any discharge diagnosis (i.e., principal, related or associated diagnosis) of arterial thromboembolic event (ischemic stroke or transient ischemic attack or systemic arterial embolism) during the 6 weeks preceding the first date of OAC delivery
 
ICD-10 codes: I63 (ischemic stroke) except I63.6 (cerebral infarction due to cerebral venous thrombosis, non-pyogenic), G45 (transient ischemic attack), I74, N28, D73.5, K76.3 (systemic arterial embolism).
 
Equals to "No" in other cases

Then, all the variables representing the exclusion criteria will be derived for each AF patients included after the inclusion criteria and the application of the algorithm ([Table IV](#)).

Table IV. Derived variable for the selection of the population – Exclusion criteria

Variable	Definition
Valvular pathology	
Binary variable (Yes/No)
 
Equals to "Yes" if the patient is hospitalized at least once with any discharge diagnosis (i.e., principal, related or associated diagnosis) of valve disease or valve surgery, during historical or inclusion period
 
ICD-10 codes: I05.x, I06.x, I07.x, I08.x, I09.x, I34.x, I39.x
 
CCAM codes (valve surgery): DBAF003, DBAF002, DBAF005, DBAF004, DBAF001, DBPA002, DBPA004, DBPA005, DBPA006, DBPA007, DBMA008, DBMA012, DBMA003, DBMA002, DBMA011, DBKA004, DBKA008, DBKA007, DBKA012, DBKA010, DBKA005, DBKA002, DBKA006, DBKA003, DBKA001, DBKA011, DBKA009, DBMA007, DBMA013, DBMA005, DBMA009, DBMA010, DBMA006, DBMA001, DBMA015, DBMA004, DBLF009, DBLF001, DBLA004, DBBF198, DBSF001, DBEA001.
 
Equals to "No" in other cases

Standard SNDS exclusion criteria	
Binary variable (Yes / No)
 
See Data Management Plan in section Error! Reference source not found.

Moreover, all the variables used to define the sub-populations will be derived for each patient selected in the study population ([Table V](#)).

Table V. Derived variables for the selection of the populations – Sub-populations

Variable	Definition
Age ≥ 80 years old	
Binary variable (<80 years old / ≥ 80 years old)
 
Derived based on the date of birth attributed to the patient after cleaning the data extraction
 
Equals to:
 
 13. “<80 years old” if the absolute difference between the year of index date and the year of birth is strictly lower than 80 years old 14. “≥ 80 years old” if the absolute difference between the year of index date and the year of birth is upper than 80 years old 
See also Data Management Plan in section Error! Reference source not found.

History of coronary arterial disease (CAD)	
Binary variable (Yes / No)
 
Equals to “Yes” if the patient meets any criterion below on or in the 2 years prior to the index date:
 
 15. Is hospitalized with any diagnosis (i.e., main, related or associated diagnosis) of coronary arterial disease 
ICD-10 codes: I21.x, I22.x, I24.x, I25.x
 
OR
 
 – Is covered by the LTD status for coronary arterial disease at least one day 
ICD-10 codes: I21.x, I22.x, I24.x, I25.x
 
Equals to “No” in other cases

Claims-based Frailty Index (CFI) (for frail patients’ derivation)	
Continuous variable (between 0 and 1)
 
Claims-based frailty index (CFI) estimates a deficit-accumulation frailty index from a clinical assessment using International Classification of Diseases (ICD) diagnosis codes, Current Procedural Terminology (CPT) codes, and Healthcare Common Procedure Coding System (HCPCS) codes in the prior 2 years in administrative claims data.
 
See more details on calculation of CFI in Appendix 22

Frail patients	
Binary variable (Yes / No)
 
Equals to “Yes” if the Claims based Frailty Index (CFI) is upper or equal to 0.20
 
See Table I variable Claims based Frailty Index (CFI)

Active cancer	Binary variable (Yes / No)

Equals to “Yes” if the patient meets any criterion below in the 2 years before index date:
 
16. Is hospitalized with any discharge diagnosis (i.e., main, related or associated diagnosis) of active cancer
 
ICD-10 codes: C00.x to C80.x, D00.x to D09.x, D37.x to D48.x, Z51.0, Z51.1
 
OR
 
 – Is covered by the LTD status for active cancer at least one day 
ICD-10 codes: C00.x to C80.x, D00.x to D09.x, D37.x to D48.x, Z51.0, Z51.1
 
Equals to “No” in other cases
	
Previous stroke	
Binary variable (Yes / No)
 
Equals to “Yes” if the patient meets any criterion below on or in the 2 years prior to the index date:
 
17. Is hospitalized at least once with any discharge diagnosis (i.e., main, related or associated diagnosis) of stroke (ischemic or haemorrhagic)
 
ICD-10 codes: I60.x, I61.x, I62.9, I63.x, I64.x, G45.x, G46.x, G81.x, S06.4, S06.5, S06.6
 
OR
 
 – Is covered by the LTD status for stroke (ischemic or haemorrhagic) at least one day 
ICD-10 codes: I60.x, I61.x, I62.9, I63.x, I64.x, G45.x, G46.x, G81.x, S06.4, S06.5, S06.6
 
Equals to “No” in other cases

Moreover, all the variables used to define stratification groups will be derived for each patient selected in the study population ([Table VII](#)).

Table VI. Derived variables for the selection of the population – Stratifications

Variable	Definition
Age groups	Categorical variable (<80, 80-90, >90 years old) See Table III
Heart failure history (for Modified CHAD ₂ DS ₂ VASC score strata derivation)	Binary variable (Yes / No) Derived based on (24)

Equals to "Yes" if the patient meets any criterion below on or in the 2 years prior to the index date:

- Is hospitalized at least once with any diagnosis (i.e., main, related or associated diagnosis) of cardiac failure

ICD-10 codes: I50.x, I11.0, I13.0, I13.2, I13.9

OR

- Is covered by the LTD status for cardiac failure at least one day

ICD-10 codes: I50.x, I11.0, I13.0, I13.2, I13.9

Equals to "No" in other cases

Hypertension history (for Modified CHAD ₂ DS ₂ VASC score strata derivation)	Binary variable (Yes / No) Derived based on (24) Equals to "Yes" if the patient meets any criterion below on or in the 2 years prior to the specified date:
	
 - Is hospitalized with any diagnosis (i.e., main, related or associated diagnosis) of hypertension 
ICD-10 codes: I10.x, I11.x, I12.x, I13.x, I15.x, I67.4
 
OR
 
 - Is covered by the LTD status hypertension at least one day 
ICD-10 codes: I10.x, I11.x, I12.x, I13.x, I15.x, I67.4
 
OR
 
 - Has reimbursements for at least 3 dispensations at pharmacy of any antihypertensive drug 
ATC codes: C02AB02, C02AC01, C02AC02, C02AC05, C02AC06, C02CA01, C02CA02, C02CA06, C02DC01, C02LA01, C03AA01, C03AA03, C03BA04, C03BA10, C03BA11, C03BX03, C03CA01, C03CA02, C03CA03, C03DA01, C03DA02, C03DA04, C03DB01, C03EA, C03EA01, C03EA04, C03EB01, C07AA02, C07AA03, C07AA05, C07AA06, C07AA07, C07AA12, C07AA15, C07AA16, C07AA23, C07AB02, C07AB03, C07AB04, C07AB05, C07AB07, C07AB08, C07AB12, C07AG01, C07AG02, C07BA02, C07BB02, C07BB03, C07BB07, C07BB12, C07CA03, C07DA06, C07FB02, C07FB03, C08CA01, C08CA02, C08CA03, C08CA04, C08CA05, C08CA06, C08CA08, C08CA09, C08CA11, C08CA13, C08CX01, C08DA01, C08DB01, C08EA02, C09AA01, C09AA02, C09AA03, C09AA04, C09AA05, C09AA06, C09AA07, C09AA08, C09AA09, C09AA10, C09AA13, C09AA15,

	C09AA16, C09BA01, C09BA02, C09BA03, C09BA04, C09BA05, C09BA06, C09BA07, C09BA09, C09BA15, C09BB02, C09BB04, C09BB10, C09CA01, C09CA02, C09CA03, C09CA04, C09CA06, C09CA07, C09CA08, C09DA01, C09DA02, C09DA03, C09DA04, C09DA06, C09DA07, C09DA08, C09DB01, C09DB02, C09DB04, C09XA02, C09XA52, C10BX03
	OR
	
 - Has reimbursements for 2 dispensations at pharmacy of any antihypertensive drug, of which at least one in a package containing >80 pills 
ATC codes: C02AB02, C02AC01, C02AC02, C02AC05, C02AC06, C02CA01, C02CA02, C02CA06, C02DC01, C02LA01, C03AA01, C03AA03, C03BA04, C03BA10, C03BA11, C03BX03, C03CA01, C03CA02, C03CA03, C03DA01, C03DA02, C03DA04, C03DB01, C03EA, C03EA01, C03EA04, C03EB01, C07AA02, C07AA03, C07AA05, C07AA06, C07AA07, C07AA12, C07AA15, C07AA16, C07AA23, C07AB02, C07AB03, C07AB04, C07AB05, C07AB07, C07AB08, C07AB12, C07AG01, C07AG02, C07BA02, C07BB02, C07BB03, C07BB07, C07BB12, C07CA03, C07DA06, C07FB02, C07FB03, C08CA01, C08CA02, C08CA03, C08CA04, C08CA05, C08CA06, C08CA08, C08CA09, C08CA11, C08CA13, C08CX01, C08DA01, C08DB01, C08EA02, C09AA01, C09AA02, C09AA03, C09AA04, C09AA05, C09AA06, C09AA07, C09AA08, C09AA09, C09AA10, C09AA13, C09AA15, C09AA16, C09BA01, C09BA02, C09BA03, C09BA04, C09BA05, C09BA06, C09BA07, C09BA09, C09BA15, C09BB02, C09BB04, C09BB10, C09CA01, C09CA02, C09CA03, C09CA04, C09CA06, C09CA07, C09CA08, C09DA01, C09DA02, C09DA03, C09DA04, C09DA06, C09DA07, C09DA08, C09DB01, C09DB02, C09DB04, C09XA02, C09XA52, C10BX03

Age groups (for Modified CHAD ₂ DS ₂ VASC score strata derivation)	Categorical variable (<65, 65-74, ≥75 years old) See Table III
Diabetes history (for Modified CHAD ₂ DS ₂ VASC score strata derivation)	Binary variable (Yes / No) Derived based on (24) Equals to "Yes" if the patient meets any criterion below on or in the 2 years prior to the index date:

- Is hospitalized with a main or related diagnosis of diabetes
ICD-10 codes : E10.x, E11.x, E12.x, E13.x, E14.x

OR

- Is hospitalized with the two criteria:
 - o A main or related diagnosis of complication of diabetes
ICD-10 codes: G59.0, G63.2, G73.0, G99.0, H28.0, H36.0, I79.2, L97, M14.2, M14.6, N08.3

AND

- o A significant associated diagnosis of diabetes
ICD-10 codes : E10.x, E11.x, E12.x, E13.x, E14.x

OR

- Is covered by the LTD status for diabetes at least one day
ICD-10 codes : E10.x, E11.x, E12.x, E13.x, E14.x

OR

- Has reimbursements for at least 3 dispensations at pharmacy of any glucose-lowering drug
ATC codes: A10Axx, A10Bxx excepted for A10BX06

OR

- Has reimbursements for 2 dispensations at pharmacy of any glucose-lowering drug, of which at least one in a package containing >80 pills
ATC codes: A10Axx, A10Bxx excepted A10BX06

Equals to "No" in other cases

